1.1 Purpose

We plan to conduct a multi-site randomized controlled trial of motivational interviewing (MI) training for physical therapists (PTs) and occupational therapists (OTs) who treat people with SCI during inpatient rehabilitation. We will test whether patients treated by MI trained PTs and OTs demonstrate greater participation in therapy sessions and better functional, social, and educational/occupational outcomes relative to patients treated by therapists without MI training. This stage of research is appropriate because a Neilsen Foundation funded pilot study that we recently completed had promising results. Study results showed that SCI patients treated by MI trained PTs and OTs participated significantly more actively in therapy sessions compared to controls. However, the study had several limitations that need to be addressed to produce a more definitive and influential trial. First, the study was conducted at a single site and results may not generalize to other sites. Second, we did not examine whether MI training and improved participation resulted in patients having better clinically meaningful outcomes such as higher likelihood of discharge to home or superior functional, social, or educational/occupational outcomes. Third, therapists trained in MI achieved only minimal competency in MI skills. We hypothesize that if therapists received ongoing coaching to improve their MI

skills during the trial the positive impact on patient participation and other outcomes might be even more robust.

1.2 Project Aims:

1. To determine whether inpatients with SCI/D treated by PTs and OTs who receive MI training and coaching demonstrate greater therapy participation compared to those treated by therapists who do not receive MI training and coaching.
2. To determine whether inpatients with SCI/D treated by PTs and OTs who receive MI training and coaching demonstrate greater functional improvement at discharge from inpatient rehabilitation and greater community integration at 6 months after discharge compared to those treated by therapists who do not receive MI training and coaching.
3. To document an effect of training and coaching on MI skills and explore potential moderators and mediators of the effect of the intervention on therapy participation.

1.3 Background and rationale

Patient participation in physical and occupational therapy during inpatient spinal cord injury (SCI) rehabilitation is not always optimal. The cost of suboptimal participation is that patients with SCI experience significantly poorer outcomes in important functional domains such as whether the person discharges to home, their functional mobility at discharge from inpatient rehabilitation and at one-year, social integration, and whether they return to work or school one year after SCI. As such, the problem of suboptimal participation in inpatient therapies represents a critical gap in the field of SCI rehabilitation that merits increased attention. Therapy participation is a biopsychosocial phenomenon and strength of participation has downstream effects on physical, social, and occupational functioning. An intervention that improved therapy participation and then led to more people being discharged to home environments, returning to work or school, and having better functional and social integration outcomes could be quite beneficial based on the number of people affected and the importance of the results.

Motivational interviewing is an evidence-based counseling style found to be effective in fostering positive health behavior change, including adherence to treatment in 119 randomized controlled trials and multiple meta-analyses.(Lundahl, 2010) MI counseling consists of five major skills: open-ended questions, affirmations, reflective listening, summarization and providing information and advice with permission. There is no theoretical framework for MI, but it is most closely associated with Self-Determination Theory (Deci & Ryan). Self-determination theory focuses on supporting intrinsic motivation, self-regulation and mental health in social contexts and posits that intrinsic motivation and self-regulation require competence, relatedness and autonomy.

In our pilot study, “Training Therapists in Motivational Interviewing to Enhance Rehabilitation Participation for SCI” (STU00204701), we recruited 62 inpatients with SCI/D to participate in the project. Patient participation in therapy was scored by therapists, the patients themselves, and a blinded project coordinator (researcher). In general, patients with SCI/D improved their therapy participation from Week 1 to Week 4. Multi-level modeling analysis revealed that patients treated by MI trained therapists scored significantly higher on the Pittsburgh Rehabilitation Participation Scale (PRPS) ($M=4.26$, $SD=0.91$) compared to controls ($M=3.79$, $SD=1.15$) after controlling for sex, age, and trauma type. The effect size was medium according to Cohen’s d at 0.56. Patients in the MI intervention group had a flatter slope of PRPS improvement than patients in the control group across time. Patient-rated and therapist-rated PRPS scores had similar trends as researcher-rated PRPS despite less significant difference. Therapist-rated PRPS showed significant group difference between groups (MI intervention group had higher scores), but no difference was noted across Week 1 to Week 4. We aim to build on these initial outcomes by providing additional MI coaching to the trained therapists and recruiting a larger sample.

This is a multi-site project with two sites, Shirley Ryan AbilityLab and Baylor Scott White, each of which will follow the same protocol under review of their local IRBs. This protocol only covers research activities at SRALab requiring Northwestern IRB approval. Any data shared between researchers at SRALab and Baylor for analysis and/or quality assurance will be deidentified.

2.0 Enrollment Criteria:

2.1 **Occupational and Physical Therapist** participants will be recruited from the inpatient spinal cord injury units at Shirley Ryan Ability Lab. They will be recruited at staff meetings and through email communication by the research team through coordination with allied health managers. During the staff meeting, the verbal therapist recruitment script will be read. An informational flyer will also be available. Recruitment emails will be sent out to the therapist listserv and followed up with each therapist individually.

Therapist inclusion criteria:

- Inpatient therapist specializing in spinal cord injury patients for at least 3 months;
- Practicing on one of the two designated SCI inpatient units at SRALab (Floor 21 or 22);
- Willing to audio record conversations during regularly-scheduled rehabilitation therapy sessions with patients;

- Willing and able to participate in 16 hours of MI training; and
- Willing to receive feedback on MI skills.

Therapist exclusion criteria:

- Inability to speak and understand English
- Inpatient therapist specializing in spinal cord injury patients for less than 3 months; and
- Unwilling or unable to follow the study protocol

2.2 **Patients with SCI** will be recruited using participating therapists' caseloads and randomly selecting participants to be approached about participating in the study. When approached, patients will be read the patient recruitment script.

Patient Inclusion Criteria:

- Adults (18+)
- Presence of a traumatic or non-traumatic spinal cord injury
- Inpatient in the spinal cord injury unit of SRALab
- Has a physical or occupational therapist who is a participant in the study

Patient Exclusion Criteria:

- Inability to speak and understand English
- Cognitive deficits
- Unwilling to allow for therapy sessions to be recorded

3.0 Sample Size:

3.1 Local sample size

We expect to enroll 90 participants at SRALab: 6 occupational or physical therapists plus 84 of their patients with SCI (of which $n = 18$ patients will only be enrolled as audio-only test participants).

The recruitment breakdown and timeline is as follows:

- Recruitment phase 1: 6 occupational or physical therapists
- Recruitment phase 2: 12 patients with SCI, 2 patients per therapist, will be recruited as audio-only test participants to assess baseline motivational interviewing skills prior to therapist randomization and training.
- Recruitment phase 3: Half ($n = 3$) of the therapists at each site will be trained in MI, so we will recruit 6 additional patients (2 per MI-trained therapist) as audio-only test participants to assess MI competency during the initial MI training phase.
- Recruitment phase 4: We will recruit 60-66 patients with SCI—10-11 patients per enrolled therapist—for the experimental phase, which includes audio recording of therapy sessions plus two additional questionnaires.

3.2 Total sample size

Across sites, we expect to enroll 180 participants: 12 OT/PT's (6 per site) and 168 patients with SCI (84 per site).

3.3 Sample size justification

We anticipate a sufficient number of patients; full time therapists are budgeted to work with six patients daily while half time therapists are budgeted to work with three patients daily.

The effect size obtained from the pilot study was 0.56 (Cohen's *d*). Based on the G*Power 3.1.9.6 program we would need to study 104 patients (52 per group) to adequately power the study assuming an alpha level of .05, power = .80, two-tailed test, and 1:1 allocation. We anticipate 20% attrition rate leading to a total of 126 patient participants.

4.0 Recruitment and Screening Methods:

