[name], with research staff in the Center for Rehabilitation Outcomes Research, previously led a pilot randomized controlled trial of MI training for PTs and OTs to improve patient participation during SCI rehabilitation. The study was a single site randomized controlled study in which seven therapists were randomized to a MI training condition and seven were randomized to a no training control condition. After PTs and OTs were trained, the study enrolled and followed 62 patients undergoing inpatient rehabilitation for SCI/D. The main outcome of the study was independently rated patient participation in therapy sessions using the PRPS. The results of the study were promising. Analyses revealed a significant group effect (patients treated by MI trained therapists scored significantly higher on the PRPS ($M = 4.26$, $SD = 0.91$) compared to controls ($M = 3.79$, $SD = 1.15$) after controlling for sex, age, and trauma type. The Cohen's d was 0.56, which is a medium effect. Analyses also showed a group x time effect based on adjusted and unadjusted models (adjusted odds ratio = 0.35, $p < .01$). MI training had a larger effect relative to controls during the first 1-2 weeks while

PRPS scores converged by week 4. There was a significant time effect with PRPS scores improving over time, particularly in the control group (adjusted odds ratio = 2.36, $p < .01$).

Motivational interviewing is an evidence-based approach to behavior change counseling demonstrated to be effective in multiple meta-analyses. [name] is an expert in motivational interviewing and has used it successfully in previous physical activity and behavior change trials. [name] is an experienced trainer and a member of the international MI Network of Trainers (MINT). [name], also an experienced trainer and member of the MINT, will assist her with the training. Fidelity to the treatment protocol will be assured through education, specific training in protocol related procedures and practicing and troubleshooting the procedures in role-plays with staff in the intervention group. During the trial, [name] will assure fidelity through completion of session content and via review of audiotaped sessions for MI skill.

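### The pilot effect size of 0.56 behind the sample size does not follow from the pilot means and SDs printed with it, which give about 0.45; if those SDs are on the analysed scale, 104 patients give about 63% power, not 80%

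*Protocol*

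**What the plan says.** Protocol Section 3.3 takes its planning value from the pilot: "The effect size obtained from the pilot study was 0.56", identified there as Cohen's d. It then reports that "we would need to study 104 patients (52 per group) to adequately power the study". The settings behind that number are 80% power, a two-sided alpha of 0.05 and equal group sizes. Attrition is added on top: "We anticipate 20% attrition rate leading to a total of 126 patient participants".

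The pilot results appear twice, in Section 1.3 and again in Section 21.0, with the same numbers: mean PRPS 4.26 (SD 0.91) for patients of MI-trained therapists and 3.79 (SD 1.15) for controls. Both places describe the comparison as adjusted for sex, age and type of trauma, and both give d = 0.56 alongside it. Section 1.3 attributes the result to a multi-level model. Neither place says which difference or which SD was used to form d. The pilot had 62 patients, and the number per arm is not given.

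**The concern.** Cohen's d is a difference in means divided by an SD. When a protocol prints two means, two SDs and a d together, the d should follow from the other four figures, or the text should say why it does not. Here it does not follow, and no reason is given.

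The 104 and 126 patient targets, and the statement that the study is adequately powered for therapy participation (Aim 1), all rest on this one value. If the effect on the analysed scale is nearer 0.45, the stated 80% is not delivered, even under the simple independent-patient calculation that the protocol uses.

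**Working it through.** **Inputs.** Pilot means 4.26 and 3.79, and SDs 0.91 and 1.15 (Sections 1.3 and 21.0). Planning d 0.56, two-sided alpha 0.05, power 0.80, 1:1 allocation, 52 per group, 126 enrolled (Section 3.3).

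**Step 1. Reproduce the plan's figure.** Section 3.3 names the software but not the test. A two-sample t-test with the noncentral t distribution at d = 0.56 gives 79.97% power with 51 per group and 80.7% with 52 per group. The stated 52 per group (104) is therefore reproduced. The calculation is sound, and the question concerns only its input.

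**Step 2. Recompute d from the printed figures.**

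- Difference: 4.26 − 3.79 = 0.47.
- Pooled SD, equal arms assumed: √((0.91² + 1.15²)/2) = 1.037.
- d = 0.47/1.037 = 0.453.

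**Step 3. See whether any reasonable choice reaches 0.56.**

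- Smaller SD as divisor: 0.47/0.91 = 0.516.
- Larger SD as divisor: 0.47/1.15 = 0.409.
- Unequal pilot arms: pooling over other splits of the 62 patients keeps d between these two values (for example 0.435 at 20/42 and 0.474 at 42/20, MI arm first).
- Rounding: with equal arms, rounding of the printed figures allows 0.441 to 0.465. The most favourable combination, a difference of 0.48 over an MI-arm SD of 0.905, gives 0.53.
- SD needed for 0.56: 0.47/0.56 = 0.839, below both printed SDs.

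None of these gives 0.56.

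**Step 4. Power at the d values that the printed figures support** (same t-test, two-sided 0.05):

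| SD used | d | Power, 52 per group | Per group for 80% |
|---|---|---|---|
| Larger (1.15) | 0.409 | 54% | 95 |
| Pooled (1.037) | 0.453 | 62.9% | 78 |
| Smaller (0.91) | 0.516 | 74% | 60 |
| As planned | 0.56 | 80.7% | 52 |

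With all 126 patients and no loss (63 per group), power is about 71% at d = 0.453. It passes 80% only at the most favourable of the three values (82% at d = 0.516), and then only if nobody is lost.

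**Step 5. What would reconcile the figures.** Suppose the printed SDs describe single weekly scores and 0.56 describes the mean of four weekly scores. The SD of that mean is the single-score SD times √((1 + 3r)/4), where r is the within-patient correlation. Setting √((1 + 3r)/4) = 0.839/1.037 gives r of about 0.54. The protocol states neither this basis nor any correlation.

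These powers treat patients as independent, as the calculation in Section 3.3 does. Clustering by therapist and the attrition allowance are separate matters.

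**The case against.** The strongest reply is that 0.56 was never meant to be the raw difference over the raw SD. Section 1.3 cites multi-level modelling with covariate control, and Section 21.0 reports adjusted odds ratios (0.35 and 2.36), so at least part of the pilot analysis was on another scale. A d built from an adjusted difference or a residual SD need not equal 0.47/1.037. An SD of 0.84 would mean that about 35% of the variance had been removed (1 − 0.839²/1.037²) by averaging, time and covariates together, and the documents do not exclude that. Section 8.4 also says that this trial's weekly PRPS scores will be averaged before analysis, and a correlation of 0.54 between ratings of one patient is not extreme. On that reading 0.56 could suit this endpoint and 0.45 would understate it.

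This part of the reply stands. A reader might infer that 0.56 is a proven error and that the trial simply has 63% power. The documents do not support that, because they do not say whether the printed SDs are patient-level SDs of the averaged score. A misprinted mean or SD beside a correct d is also possible.

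The reply does not remove the contradiction. The protocol gives no other difference or SD for 0.56 and places it directly beside figures that do not produce it. An adjusted or averaged-score d can be used in a two-sample formula as an approximation, but only if the planned analysis is on the same scale, and Section 3.3 does not say that it is.

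A second reply is that Section 1.1 expects a stronger effect because coaching is added, so 0.56 could be defended as a target. Section 3.3 does not argue this. It presents 0.56 as the effect that the pilot obtained.

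**Conclusion.** The point holds as an unreconciled contradiction between the planning effect size and the pilot data printed to support it. The printed means and SDs give d of about 0.45, with 0.41 to 0.52 covering any arm split or choice of SD, and 0.53 at the extreme of rounding.

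The consequence for power is conditional. If the printed SDs are patient-level SDs of the analysed PRPS score, and under the two-sample t-test that reproduces 52 per group, 104 evaluable patients give about 63% power (54% to 74%) rather than 80%. If 0.56 has a documented basis on the scale that will be analysed, the 104 stands for that value and only the reporting needs repair. In both cases the text needs correcting, because a reader cannot obtain the planning value from the data shown.

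**What to change.** Reconcile Section 3.3 with the pilot results in Sections 1.3 and 21.0, in one of two ways:

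1. If 0.56 came from an adjusted model or a four-week mean, print the difference and SD that produce it, say what the printed SDs of 0.91 and 1.15 describe, and state in Section 3.3 that the planned analysis uses that same scale. If a printed mean or SD is a misprint, correct it in both places.
2. If no such basis exists, replace 0.56 with 0.45 (0.47/1.04) in all three sections. State in Section 3.3 that 104 evaluable patients give about 63% power under the stated calculation, and that 80% is reached only at d of about 0.56.

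The change is a few sentences and no added patients are requested. The cost is that the stated power may become less favourable.

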- Once the research team enrolls 6 physical therapists or occupational therapists, demographic information will be collected by the research assistant via REDCap survey (see 'DemographicSurvey' under 'supporting documents'). The therapist participant may fill out the demographic survey via REDCap themselves if they prefer – the research assistant will review the answers and follow up with participants in-person to clarify as needed..
- All therapists will audio record two therapy sessions with SCI/D patients wearing a digital recorder on their name badge lanyard or on their clothing. This will provide a baseline level of MI skills. Audio-only test patients will sign an authorization to have their therapy session recorded (see "EditedSRAlabAudioConsentForm"). We will not obtain full informed consent from the audio-only patients because their identities will not be recorded and they will not participate in the patient questionnaires described below. The test audio recordings obtained in steps 8.1 and 8.2 will be destroyed after therapists' motivational interviewing skills are assessed.
- After all baseline recordings are complete, the data manager will perform a central computer-generated randomization and then transmit treatment allocation to [name], the MI trainer, via secure email. [name] will then contact enrolled PTs and OTs at each site to set up training as indicated. Randomization will be stratified based on therapist type (PT vs.

OT). The allocation sequence will be concealed from any study staff involved in enrollment of participants or data collection via a restricted access database program.

- Half of the therapists will be assigned to the experimental Motivational Interviewing group, and the other half will be assigned to the control group.

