8.3 Recruit participants – Inpatients with SCI

- Once the MI trained PTs and OTs achieve basic MI competency, the experimental phase of the study will begin. The research assistants at both sites will approach a convenience sample of eligible inpatients that the PTs and OTs in the study are treating, for participation in the study. The research assistants will recruit and consent 10-11 inpatients for each of the therapists who were trained in MI as well as for each of the therapists who were not trained in MI for a total of 126 inpatients.

- The research assistants will ask the therapists when they feel comfortable to add another patient participant to their research caseload so as not to overburden the therapist with the research tasks. The patients will be kept blinded to whether their therapist has been trained in MI or not.

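### The 104/126-patient calculation treats patients as independently randomised, but only 12 therapists are randomised, so the stated 80% power is not delivered

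*Protocol*

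**What the plan says.** Protocol section 3.3 bases the sample size on the pilot: "The effect size obtained from the pilot study was 0.56" as Cohen's d. From G*Power it concludes that "we would need to study 104 patients (52 per group) to adequately power the study assuming an alpha level of .05, power = .80", with a "two-tailed test, and 1:1 allocation". It then allows for 20% attrition and arrives at 126 patients.

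The design is set out elsewhere. Section 8.1 randomises therapists, stratified by PT or OT: "Half of the therapists will be assigned to the experimental Motivational Interviewing group, and the other half will be assigned to the control group". Section 3.2 gives the totals as "12 OT/PT's (6 per site) and 168 patients with SCI (84 per site"), and section 3.1 has three therapists trained at each site, so there are six per arm overall. Section 8.3 recruits "10-11 inpatients for each of the therapists who were trained in MI" and the same number for each control therapist.

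The pilot was also randomised by therapist. Section 21.0 reports that "seven therapists were randomized to a MI training condition and seven were randomized to a no training control condition", and section 1.3 says its data were analysed by multi-level modelling.

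**The concern.** The calculation in section 3.3 is for a trial that randomises 104 patients one by one. This trial randomises 12 therapists, and the treatment reaches patients through the therapist's skill, which the protocol rates and coaches therapist by therapist. Patients of one therapist share that skill, along with the therapist's style and caseload, so their participation scores are likely to be correlated. Two consequences follow:

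- Each further patient of the same therapist adds less information than an independent patient would.
- The arm effect is judged against variation between 12 therapists, so the error df are about 12 - 2 = 10, not 104 - 2 = 102.

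The pilot analysis recognised this structure, but none of it carries into the sizing. The new trial also randomises fewer therapists (12) than the pilot did (14), so the rise from 62 to 126 patients buys less than the headcount suggests.

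Aim 1 is at stake. A valid analysis would have materially less power than stated, and a null result could be misread as evidence against the training. An analysis that matched the sizing would exceed its nominal 5% error rate.

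**Working it through.** **Inputs from the protocol.** d = 0.56, two-sided alpha 0.05, power 0.80, 1:1 allocation, 104 evaluable, 20% attrition and 126 enrolled (section 3.3); 12 therapists (section 3.2), 6 per arm; 10-11 patients per therapist (section 8.3; 126/12 = 10.5).

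**Assumed.** The within-therapist ICC is not given, so a range from 0 to 0.20 is shown. d is taken as standardised on the total SD of the patient-level score.

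**Step 1: reproduce 104.** For a two-sample t-test on independent patients, the noncentrality is d·√(N/4) on N - 2 df. With N = 104 this is 0.56 × √26 = 2.855 on 102 df, which gives power 0.807. With N = 102 power is 0.7997, just short of 0.80. So 104 is exactly the independent-patient answer and contains no allowance for clustering.

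**Step 2: patients left after attrition.** 126 × 0.8 = 100.8, or 100.8/12 = 8.4 per therapist.

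**Step 3: add the therapist level.** Design effect DE = 1 + (8.4 - 1) × ICC. Noncentrality = 0.56 × √(100.8/(4 × DE)). The test uses t on 10 df (critical value 2.228). For example, at ICC 0.05 DE = 1 + 7.4 × 0.05 = 1.37, the effective sample is 100.8/1.37 = 73.6, the noncentrality is 0.56 × √(73.6/4) = 2.40, and power is 58%.

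The last column is the error rate if patients were analysed as independent, approximated by 2 × (1 - Φ(1.96/√DE)).

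| ICC (assumed) | DE | Effective N | Power, 10 df | Power, patient-level df | Type I error, patient-level test |
|---|---|---|---|---|---|
| 0 | 1.00 | 100.8 | 72% | 80% | 5% |
| 0.01 | 1.07 | 93.9 | 69% | 77% | 6% |
| 0.02 | 1.15 | 87.8 | 66% | 74% | 7% |
| 0.05 | 1.37 | 73.6 | 58% | 66% | 9% |
| 0.10 | 1.74 | 57.9 | 49% | 56% | 14% |
| 0.20 | 2.48 | 40.6 | 37% | 42% | 21% |

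A simulation (8,000 runs, 6 therapists per arm, 8-9 patients each, ICC 0.05) agrees: 57% power for the therapist-level test and 9.5% type I error for the patient-level t-test.

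**Step 4: sensitivity to the number evaluable (10 df).**

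| Evaluable | ICC 0 | ICC 0.02 | ICC 0.05 | ICC 0.10 | ICC 0.20 |
|---|---|---|---|---|---|
| 100.8 | 72% | 66% | 58% | 49% | 37% |
| 104 | 73% | 67% | 59% | 49% | 37% |
| 126 (no loss) | 81% | 74% | 65% | 53% | 39% |

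**Step 5: what the planned size can detect.** With 100.8 patients and 10 df, the effect detectable with 80% power is d = 0.66 at ICC 0.02, 0.73 at 0.05 and 0.82 at 0.10.

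**Step 6: what would restore 80%.** With 12 therapists kept, 80% power at d = 0.56 needs 156 evaluable patients at ICC 0.02 and 252 at ICC 0.05. As the number of patients per therapist grows without limit, the noncentrality tends to 0.56 × √(12/(4 × ICC)). At ICC 0.10 that is 0.56 × √30 = 3.07, or 79% power, so no number of patients is enough. At 8.67 evaluable patients per therapist (104/12), the need is 8 therapists per arm at ICC 0.02, 10 at 0.05 and 12 at 0.10.

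**The case against.** The strongest reply is that the size of the shortfall depends on an ICC the protocol does not give, and on how many patients yield data for Aim 1. Both points are fair. The participation scale is rated during the four-week inpatient period, while the 20% loss may mainly concern the 6-month follow-up; section 3.3 does not say which. If all 126 patients were evaluable and the ICC were zero, power on 10 df would be 81%. At ICC 0.02 it would already be 74%, so a small ICC removes that margin.

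The scale of d = 0.56 is also unclear. It is reported beside a covariate-adjusted multi-level result, while the printed means and SDs give (4.26 - 3.79)/√((0.91² + 1.15²)/2) = 0.45. True power could therefore be higher or lower than tabulated, and the percentages are illustrative. A multi-level origin of d does not repair the calculation, because a standardised effect carries no design effect. Averaging the weekly scores reduces noise within patients but does not remove variation between therapists.

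A statistical analysis plan may well model therapist as a cluster, and the protocol nowhere commits to a patient-level t-test. The type I error figures are therefore conditional on an analysis that mirrors the sizing. A correct model would protect the error rate, but it would not restore power to a sample size fixed here.

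Finally, fitting site and therapist type leaves 12 - 4 = 8 df rather than 10. This lowers power by 1 to 3 points (for example 56% instead of 58% at ICC 0.05), before any credit for therapist variation that those terms explain. It does not change the conclusion.

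**Conclusion.** The point holds. The G*Power arithmetic is correct for independently randomised patients, but that is not this design, so the 80% in section 3.3 is wrong as written. Under the protocol's own effect size and attrition, a test on 10 df has about 66% power at ICC 0.02, 58% at 0.05 and 49% at 0.10. With 100.8 or 104 evaluable patients it is below 80% even at ICC 0 (72% and 73%), so at those numbers the direction does not rest on the ICC, only the size does. These figures assume d = 0.56 on the total-SD scale and equal caseloads. The correction must be made, because the power claim for Aim 1 depends on it.

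**What to change.** Replace the calculation in section 3.3 with one for 12 randomised therapists, six per arm. It should:

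- state an ICC and its source, ideally the pilot's own multi-level model, and show a range around it;
- apply the design effect 1 + (m - 1) × ICC, with m the evaluable patients per therapist;
- use therapist-level df: 10, or 8 if site and therapist type are fitted;
- restate the power, or the effect detectable with 80% power, at the planned size.

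One added sentence should say that the arm effect is tested with therapist as a random effect and a small-sample df method (Kenward-Roger or Satterthwaite), not with a patient-level t-test. Model details can stay in the statistical analysis plan.

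The cost is a rewritten paragraph and one sentence, with no extra patients; the stated power becomes less favourable. If the sponsor wants to keep 80% at d = 0.56, the effective lever is more therapists rather than more patients per therapist. That is a separate decision with real cost, best taken with the corrected figures in view.
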